5.3 OPEN-LABEL EXTENSION TREATMENT PERIOD

Subjects who complete the 48-week double-blind, placebo-controlled treatment period will be rolled over into the 48-week open-label extension period in which all subjects will receive active treatment with lademirsen (SAR339375) 110 mg QW. Subjects who complete the double-blind, placebo-controlled treatment period but who will not continue with the open-label extension will enter directly into the post-treatment follow-up period (see [Section 5.5](#)).

The open-label treatment period allows all the subjects to benefit from exposure to lademirsen (SAR339375) after the randomized period of the treatment. In addition, this allows us to gain long-term safety and efficacy data in Alport subjects. Procedures for study visits in the 48-week open-label extension will be nearly identical to those for the 48-week double-blind, placebo-controlled treatment period.

The following assessments, procedures, and data collection will be performed prior to dose administration, if not specify, at the study visits during the open-label extension treatment period:

Week 48 (±2 days) - Site Visit

The Week 48 visit of the double-blind, placebo-controlled treatment period will serve as the baseline visit of the open-label extension. Subjects continuing on to the open-label extension will receive their first open-label dose of lademirsen (SAR339375) at this visit. In addition to the procedures specified for this visit in [Section 5.2](#), vital signs will be taken both pre- and post-dose and AEs including information related to ISRs will be assessed for at least 2 hours after injection at Week 48.

Weeks: 49, 50, 51, 53, 54, 55, 57, 58, 59, 61, 62, 63, 65, 66, 67, 69, 70, 71, 73, 74, 75, 77, 78, 79, 81, 82, 83, 85, 86, 87, 89, 90, 91, 93, 94 and 95 (±2 days) - *Option for Alternative Location Visit

- CBC with differential
- Assessment of AEs including ISRs
- Injection of study drug

Week 52 (±2 days) - Site Visit

- Concomitant medications
- Vital signs and body weight
- Urinalysis
- Spot UPCR
- CBC with differential
- Coagulation panel
- Serum chemistry
- Lipid panel
- hs-CRP
- Urine pregnancy
- Assessment of AEs including ISRs
- Injection of study drug

Weeks: 56, 64, 68, 76, 80, 88, 92 (all ±2 days) - *Option for Alternative Location Visit

- Concomitant medications
- CBC with differential
- Urine pregnancy
- Spot UPCR
- Serum chemistry

- Coagulation panel
- Assessment of AEs including ISRs
- Injection of study drug

Weeks: 60, 72, 84, and 96 (all ± 2 days) - Site Visits

- Concomitant medications
- Vital signs and body weight
- Limited physical exam (symptom-directed, at Weeks 60 and 84) or complete physical exam (at Weeks 72 and 96)
- Hearing Assessment at Week 96
- 12-lead ECG
- 24-hour urine sample
- Urinalysis
- CBC with differential
- Coagulation panel
- Urine pregnancy
- Serum chemistry
- Lipid panel
- hs-CRP
- Blood sample for PK (pre-dose)
- Blood sample for complement (C3, C3a, C4 and Bb) (pre-dose)
- Blood sampling for markers of inflammation (quantitative immunoglobulins: γ -globulin, IgM, IgG)
- ADA
- Biomarkers from blood and urine samples (see [Section 10.5.2.2](#) for study conduct in China)
- miR-21
- Assessment of AEs including ISRs
- Injection of study drug (not Week 96)

5.4 EARLY TERMINATION

Any subject who discontinues before completing either active treatment period (double-blind placebo or open-label extension periods) should be encouraged to return to the study site to complete the following end-of-study procedures. With the exception of CBC, serum and urine chemistry, and coagulation panel, the specified laboratory assessments do not need to be completed if they were completed as part of a study visit within the 4 previous weeks.

- Concomitant medications
- Vital signs and body weight
- Complete physical exam
- Hearing Assessment
- 12-lead ECG
- Assessment of AEs including ISRs
- 24-hour urine sample
- Urinalysis
- CBC with differential
- Serum chemistry
- Lipid panel
- hs-CRP
- Coagulation panel
- Blood sample for PK and complement (C3, C3a, C4, and Bb)
- Blood sampling for markers of inflammation (quantitative immunoglobulins: γ -globulin, IgM, IgG)
- ADAs
- Biomarkers from blood and urine samples (for study conduct in China, see [Section 10.5.2.2](#))
- miR-21, plasma/serum storage (for study conduct in China, see [Section 10.5.2.3](#)), record adverse events
- Urine pregnancy

5.5 FOLLOW-UP PERIOD

Subjects who complete the open-label treatment extension period or subjects who discontinue early and have completed the early termination visit will enter the post-treatment follow-up period, which will be the same for all subjects. Follow-up weeks are numbered starting from the

last scheduled study visit in the active treatment period (eg, Follow-up Week 2 will occur 2 weeks after Week 96 or after ET).

Follow-up Weeks 2 and 4 (both ± 3 days) - *Option for Alternative Location Visit

- Concomitant medications
- Collection of information related to potential AEs including ISRs
- CBC with differential

Follow-up Week 10 (± 3 days) - Site Visit

- Concomitant medications
- Vital signs and body weight
- Complete physical exam
- Collection of information related to potential AEs including ISRs
- Complement (C3, C3a, C4, and Bb)
- Blood sampling for markers of inflammation (quantitative immunoglobulins: γ -globulin, IgM, IgG)
- miR-21
- Urinalysis
- CBC with differential
- Serum chemistry
- Lipid panel
- hs-CRP
- Coagulation panel
- ADAs

5.6 UNSCHEDULED VISITS

Unscheduled visits are those visits that occur beyond regularly scheduled visits and are performed in order to assess a previously noted AE (especially if the AE is considered by the Investigator to be possibly related to the use of study drug), abnormal/alarming laboratory values, and/or clinical findings. In such cases, the Investigator may at his/her discretion arrange for a subject to have an unscheduled visit. The subject will be contacted to arrange an unscheduled visit to assess the noticed abnormalities. **Only focused assessments (guided by the reason for the visit) are foreseen for these visits**, and there will be no need to collect very extensive additional laboratory or other safety and efficacy data.

The unscheduled visits could be done at alternative location (including at home), and at the Investigator's discretion, for the assessment of AEs related to abnormal/alarming laboratory values.

The Unscheduled Visit Page in the eCRF must be completed ([Table 1](#), [Table 2](#)).

5.7 ALTERNATE LOCATION VISIT

Subjects will be seen at the Investigational site, or at an Alternate Location including subject's home by trained, qualified personnel to whom the Investigator has delegated responsibility. All staff performing activities at an Alternate Location will be appropriately trained in the protocol, study drug administration, study assessments and procedures to be performed. They will be documented in the delegation of duties log. The purpose of this flexibility, where available, is to offer subjects the option of having their visits performed at a more convenient location (including the subject's home), due to the frequency of study visits and length of study, and the potential for subjects to live a significant distance from their main Investigational site.

5.8 END OF STUDY DEFINITION

The end of the study is defined as the date of the last visit of the last subject in the trial globally.

6 BACKGROUND, SAFETY, EFFICACY, PHARMACODYNAMIC, AND PHARMACOKINETIC ASSESSMENTS

The timing of procedures and assessments to be performed is provided in [Table 1](#) (for screening and the double-blind, placebo-controlled treatment period), [Table 2](#) (for the open-label treatment period), and [Section 5](#).

6.1 MEDICAL HISTORY AND FAMILY HISTORY

A subject's significant prior (eg, occurring before signing the ICF) and ongoing illnesses, surgeries, and smoking history should be documented on the eCRF Medical History Page. Medical history relevant to Alport syndrome will include past lab tests related to disease progression and should be documented on the appropriate eCRF page. Family history relevant to Alport syndrome and renal disease should be documented on the eCRF Family History Page. Medical history and family history data collected in the ATHENA study may be used for this study. Additional illnesses present from the time when the ICF is signed until the completion of the last follow-up visit are to be documented as AEs on the eCRF Adverse Event Page.

6.2 SAFETY ASSESSMENTS

Safety assessments will consist of monitoring and recording all AEs, including SAEs, physical examination, vital sign assessment, ECG recording, clinical laboratory results (hematology, serum chemistry, lipids, coagulation, complement, urinalysis), and regular monitoring of ISRs.

6.2.1 Adverse events

An AE is any undesirable sign, symptom, or medical condition occurring after signing the ICF. Information about all AEs, regardless of seriousness or relationship to study treatment, whether volunteered by the subject, discovered by questioning, or detected through physical examination, laboratory testing, or other means, will be collected and recorded on the AE eCRF page and followed as appropriate.

Medical conditions present prior to study entry will be documented in the Medical History eCRF. However, medical conditions occurring after signing the ICF are to be recorded as AEs. Treatment-emergent adverse events (TEAEs) are defined as AEs with onset after the first dose of study drug or existing AEs that worsened after the first dose of study drug until the last administration of study medication plus 10 weeks follow up.

The Investigator (or delegate) is obliged to interview subjects at each visit and clarify/discuss any abnormality that may indicate a potential AE.

Subjects should be encouraged to report AEs that occur between scheduled visits to the Investigator or between home injections to the nurse.

AEs will be recorded from the time of signing the ICF until the end of the safety follow-up. If any AE is ongoing at the time of subject withdrawal, the subject will be asked to return for clinic visits or to respond to follow-up by telephone (if the AE is considered not related or unlikely related to study drug) until resolution or stabilization of this AE.

Whenever possible, diagnosis or single syndrome should be reported instead of symptoms. The Investigator should specify the date of onset, intensity, action taken with respect to study treatment, corrective treatment/therapy given, additional investigations performed, outcome, and his/her opinion as to whether there is a reasonable possibility that the AE was caused by the study treatment. When AEs occur on the day of study drug administration, the approximate time of day should be provided.

Any AE that occurs during the study must be monitored and followed up until one or more of the following criteria have been met:

- It has resolved to \leq Grade 1 or baseline level
- Pathological laboratory findings have returned to normal
- Steady state has been achieved

A subset of AEs will be closely monitored (ie, events identified as AESIs; see [Section 6.2.2](#) and [Table 3](#)).

It is the responsibility of the Investigator to ensure that any necessary additional therapeutic measures and follow-up procedures are performed.

As far as possible, each AE will also be described by:

- Duration (start and end dates)
- Severity grade
- Relationship to the study drug
- Action(s) taken and, as relevant, the outcome

6.2.2 Adverse event of special interest

An adverse event of special interest (AESI) is an AE (serious or non-serious) of scientific and medical concern specific to the Sponsor's product or program, for which ongoing monitoring and immediate notification by the Investigator to the Sponsor is required. Such events may require further investigation in order to characterize and understand them. Adverse events of special interest may be added, modified or removed during a study by protocol amendment.

- Pregnancy of a female participant entered in a study as well as pregnancy occurring in a female partner of a male participant entered in a study with IMP:
 - Pregnancy occurring in a female participant entered in the clinical trial or in a female partner of a male participant entered in the clinical trial. It will be qualified as an SAE only if it fulfills one of the seriousness criteria (see Appendix 1 [[Section 10.1](#)]).

- In the event of pregnancy in a female participant, IMP should be discontinued.
- Follow-up of the pregnancy in a female participant or in a female partner of a male participant is mandatory until the outcome has been determined (see Appendix 4 [Section 10.4]).
- Symptomatic overdose (serious or non-serious) with IMP:
 - An overdose (accidental or intentional) with the IMP is an event suspected by the Investigator or spontaneously notified by the participant and defined as increase of at least 30% above the intended dose at each administration or any two doses separated by <5 days.
- Other specific AESIs subject to close monitoring:
 - All Grade ≥ 2 events listed in Table 3, except for eGFR
 - Grade ≥ 3 events of eGFR

6.2.3 Adverse events grading

Table 3 - Grading system for the definition of AESIs

Parameter	Mild (Grade 1)	Moderate (Grade 2)	Severe (Grade 3)	Life threatening event (Grade 4)
Platelets	125 000 to 100 000 cells/ μ L	<100 000 to 50 000 cells/ μ L	<50 000 to 25 000 cells/ μ L	<25 000 cells/ μ L
ALT or AST ^a	1.25 to <2.5 x ULN	2.5 to <5.0 x ULN	5.0 to <10.0 x ULN	≥ 10.0 x ULN
Direct Bilirubin	NA	NA	> ULN with signs and symptoms of hepatotoxicity	> ULN with life-threatening consequences (eg, signs and symptoms of liver failure)
Total Bilirubin	1.1 to <1.6 x ULN	1.6 to <2.6 x ULN	2.6 to <5.0 x ULN	≥ 5.0 x ULN
Alkaline phosphatase	1.25 to <2.5 x ULN	2.5 to <5.0 x ULN	5.0 to <10.0 x ULN	≥ 10.0 x ULN
eGFR	NA	10 to <30% decrease from participant's baseline	30 to <50% decrease from participant's baseline	$\geq 50\%$ decrease from participant's baseline or dialysis needed

ALT: alanine aminotransferase; AST: aspartate aminotransferase; eGFR: estimated glomerular filtration rate; NA: not applicable; ULN: upper limit of normal

Grading criteria are based on the DAIDS grading system (30). All deaths related to an AE are to be classified as Grade 5.

a For management of elevated aminotransferases, please refer to Section 10.3.2.

For events not defined in Table 3, the following guidelines are to be used to classify adverse events (see Table 4).

Table 4 - Classification of adverse events by severity

Parameter	Mild (Grade 1)	Moderate (Grade 2)	Severe (Grade 3)	Life threatening (Grade 4)	Grade 5
Clinical AE NOT identified in Table 3	Mild symptoms causing no or minimal interference with usual social & functional activities with intervention not indicated	Moderate symptoms causing greater than minimal interference with usual social & functional activities with intervention indicated	Severe symptoms causing inability to perform usual social & functional activities with intervention or hospitalization indicated	Potentially life-threatening symptoms causing inability to perform basic self-care functions with intervention indicated to prevent permanent impairment, persistent disability, or death	Death related to AE

AE: adverse event

Grading criteria are based on the DAIDS grading system (30).

If there is an increase in severity of an AE, it will be recorded as a single event. The worst grade of severity for the AE should be recorded in the source data and eCRF.

An AE that is assessed as severe (having a “severe” or Grade 3 classification) should not be confused with an SAE. “Severe” is a category in rating the intensity of an event. An event is defined as “serious” when it meets one of the pre-defined outcomes described in [Section 6.2.5](#).

The Investigator will assess any causal relationship of an AE to study drug not related to treatment or related to treatment.

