An event is defined as “serious” when it meets at least 1 of the predefined outcomes as described in the definition of an SAE, NOT when it is rated as severe.

Assessment of causality

- The Investigator is obligated to assess the relationship between study intervention and each occurrence of each AE/SAE.
- A “reasonable possibility” of a relationship conveys that there are facts, evidence, and/or arguments to suggest a causal relationship, rather than a relationship cannot be ruled out.
- The Investigator will use clinical judgment to determine the relationship.
- Alternative causes, such as underlying disease(s), concomitant therapy, and other risk factors, as well as the temporal relationship of the event to study intervention administration will be considered and investigated.
- The Investigator will also consult the Investigator’s Brochure (IB) and/or Product Information, for marketed products, in his/her assessment.
- For each AE/SAE, the Investigator must document in the medical notes that he/she has reviewed the AE/SAE and has provided an assessment of causality.
- There may be situations in which an SAE has occurred and the Investigator has minimal information to include in the initial report to the Sponsor’s representative. **However, it is very important that the Investigator always make an assessment of causality for every event before the initial transmission of the SAE data to the Sponsor’s representative.**
- The Investigator may change his/her opinion of causality in light of follow-up information and send a SAE follow-up report with the updated causality assessment.
- The causality assessment is one of the criteria used when determining regulatory reporting requirements.

Follow-up of AEs and SAEs

- The Investigator is obligated to perform or arrange for the conduct of supplemental measurements and/or evaluations as medically indicated or as requested by the Sponsor’s representative to elucidate the nature and/or causality of the AE or SAE as fully as possible. This may include additional laboratory tests or investigations, histopathological examinations, or consultation with other health care professionals.
- If a subject dies during participation in the study or during a recognized follow-up period, the Investigator will provide the Sponsor’s representative with a copy of any post-mortem findings including histopathology.

- New or updated information will be recorded in the originally completed CRF.

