4.7.2 Adverse events

Adverse event observation period

- **Pre-treatment adverse events** are adverse events that developed or worsened or became serious from the signed informed consent date up to the first administration of IMP.
- **Treatment-emergent adverse events (TEAE)s in placebo-controlled period:** Any adverse events that developed or worsened or became serious during the treatment-emergent placebo-control period.
- **Treatment-emergent adverse events in lademirsen treatment period:** Any adverse events that developed or worsened or became serious during the treatment-emergent lademirsen treatment period.
- **Treatment-emergent adverse events in overall study treatment period:** Any adverse events that developed or worsened or became serious during the treatment-emergent overall study treatment period.

All adverse events will be coded to a lower-level term (LLT), preferred term (PT), high-level term (HLT), high-level group term (HLGT), and associated primary system organ class (SOC) using the version of Medical Dictionary for Regulatory Activities (MedDRA) currently in effect at Sanofi at the time of database extraction or database lock.

Adverse events of special interest (AESI)

AESIs reported by the investigator in CRF will be summarized. However, if there are any eGFR grade 2 (toxicity grade 2 or intensity moderate) events retained in the clinical database as AESIs due to reporting based on old AESI grading system of the protocol, they will not be considered as AESIs at the analysis level. Only the reported AESIs which meet the applicable definition at the time of the analysis will be considered at the analysis level.

In addition, lab parameters that potentially meet the criteria in grading system for adverse events of interest table ([Table 6](#)) will be summarized separately.

Table 6 - Grading system for the definition of AESIs

Parameter	Mild (Grade 1)	Moderate (Grade 2)	Severe (Grade 3)	Life threatening event (Grade 4)
Platelets	125 000 to 100 000 cells/ μ L	<100 000 to 50 000 cells/ μ L	<50 000 to 25 000 cells/ μ L	<25 000 cells/ μ L
ALT or AST ^a	1.25 to <2.5 x ULN	2.5 to <5.0 x ULN	5.0 to <10.0 x ULN	\geq 10.0 x ULN
Direct Bilirubin	NA	NA	> ULN with signs and symptoms of hepatotoxicity	> ULN with life-threatening consequences (eg, signs and symptoms of liver failure)
Total Bilirubin	1.1 to <1.6 x ULN	1.6 to <2.6 x ULN	2.6 to <5.0 x ULN	\geq 5.0 x ULN

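### A worsening AE is kept as one record at its worst grade with no listed date of worsening, yet both documents classify treatment emergence by worsening within a period

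*Protocol*

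**What the plan says.** **Recording.** Protocol 6.2.3 has two sentences on the matter: "If there is an increase in severity of an AE, it will be recorded as a single event" and "The worst grade of severity for the AE should be recorded in the source data and eCRF". Protocol 6.2.1 lists what the site enters: "The Investigator should specify the date of onset, intensity, action taken with respect to study treatment", and so on. It then asks for duration as a start and an end date, plus a severity grade. Protocol 6.2.4 asks for a new record when the same AE recurs after an earlier episode that was resolved or resolving, not when an ongoing AE becomes more severe. For follow-up, Protocol Appendix 1 (10.1) says: "New or updated information will be recorded in the originally completed CRF".

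**Analysis.** Protocol 6.2.1 includes among treatment-emergent AEs "existing AEs that worsened after the first dose of study drug". SAP 4.7.2 defines them period by period. For the lademirsen treatment period the definition is "Any adverse events that developed or worsened or became serious during the treatment-emergent lademirsen treatment period", and the placebo-controlled period has a matching definition. The same SAP section treats worsening as one kind of onset, and it tabulates AEs by maximal severity.

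**Final analysis.** Table 1 of the SAP addendum keeps incidence and severity of treatment-emergent AEs and SAEs for both the placebo-controlled and the lademirsen treatment periods. Its laboratory, vital-sign and ECG abnormality endpoints are for the placebo-controlled period only.

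**The concern.** To apply the worsening part of either definition, the programmer needs to know when the grade changed and what it was on each side of a period boundary. The fields described in the protocol hold neither. This is more than a missing detail: the protocol tells sites to collapse the information that the analysis rule relies on.

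Two boundaries matter: the first IMP dose and, for those who roll over, the first open-label dose, where SAP 4.1 ends the placebo-controlled period. What is at stake is the safety comparison in the double-blind period and, more directly, the lademirsen-period AE table. With abnormality endpoints confined to the placebo-controlled period, that table is the only safety endpoint that the addendum lists for lademirsen exposure after crossover.

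**Working it through.** The plan states no figure on this point, so the check sets the rules side by side and then gives a scale.

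**Step 1. Where each kind of AE lands.** The second column applies the treatment-emergent definitions. The third uses only the listed fields, that is, the start date and the worst grade.

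| AE starts, then worsens | By the definitions | By start date and worst grade |
|---|---|---|
| Before first dose; worsens in the double-blind period (either arm) | Treatment-emergent, double-blind, at the higher grade | Pre-treatment, so not counted |
| Double-blind on placebo; worsens after first open-label dose | Double-blind at the lower grade, and lademirsen period at the higher grade | Double-blind at the higher grade; absent from the lademirsen period |
| Double-blind on lademirsen; worsens after first open-label dose | Double-blind at the lower grade; lademirsen period at the higher grade | Double-blind at the higher grade; lademirsen period correct |

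In rows 2 and 3 the participant already counts as having the AE in the double-blind period. Incidence there does not change; only the severity cell does. Row 2 is the only one in which an AE leaves the lademirsen-period table.

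**Step 2. Whether the date-handling rules repair this.** SAP 4.7.2 and 5.3 impute incomplete onset dates towards treatment emergence. A single record with a complete start date does not look incomplete, so nothing need trigger the imputation. If the worsening date is itself treated as missing, row 1 could be rescued. For row 2, however, SAP 5.3 sends an event whose period cannot be determined to the double-blind period, which is where the start date had put it.

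**Step 3. Scale.** Stage 1 has 43 participants randomized 2:1 (SAP 1.1).

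- Placebo: 43 × 1/3 = 14.3, about 14. Lademirsen: 43 × 2/3 = 28.7, about 29.
- One event in a placebo severity cell: 1/14 = 7.1 percentage points.
- One event in a lademirsen double-blind severity cell: 1/29 = 3.4 points.
- One event absent from the lademirsen period: 1/43 = 2.3 points if every placebo participant crossed over. With fewer crossovers the share rises, to 1/30 = 3.3 points if only one did.

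**Step 4. Direction in the double-blind table.** Assume, for illustration only, one AE per participant ongoing at rollover and 10% to 20% of these worsening afterwards. The raised severity entries would be 14 × 0.10 to 14 × 0.20 = 1.4 to 2.8 on placebo, and 29 × 0.10 to 29 × 0.20 = 2.9 to 5.8 on lademirsen. That is the same 10% to 20% of each column, so equal worsening does not shift the comparison.

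**The case against.** The strongest reply is that the documents never say treatment emergence is derived from the first start date. The SAP's definitions include worsening and its notion of onset includes a worsening date, so the intended classification is right. If the eCRF or its completion guideline captures dated grade changes, nothing is lost. This stands as a limit on the claim. A reader might infer that worsened events are in fact missed or charged to placebo; the documents support only that they can be. It does not remove the point, because the protocol text that sites follow asks for one event and its worst grade.

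The exposure is also narrow. The pre-dose case needs an AE that begins after consent, within a screening period of up to 4 weeks, is still ongoing at Day 1 and then worsens. Under Protocol Appendix 1, exacerbation of a pre-existing condition is an AE in its own right. Becoming serious is a separate trigger in SAP 4.7.2. Injection site reactions are assessed after each injection. All of this stands.

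Finally, the addendum records that the study was terminated before all Stage 1 participants completed double-blind treatment and that Stage 2 did not enrol. About 14 crossovers is therefore a ceiling, and amending the protocol would change no data. That affects the choice of remedy. It does not affect the tables still to be produced at the final lock.

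**Conclusion.** The recording rule and the treatment-emergence definitions do not fit together, and the point is live for the final analysis. Its size cannot be stated: the documents give no number of AEs spanning either boundary, and the per-event shares above are a scale, not an estimate. The conclusion assumes that the eCRF holds only the fields that the protocol describes.

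Two stronger readings are tempting and unsupported.

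- *That the error always favours lademirsen.* The pre-dose loss and the raised double-blind severity can occur in both arms, and equal worsening leaves the double-blind comparison unchanged. Only the crossover case has a fixed direction: it understates AEs on lademirsen in the lademirsen-period table.
- *That eGFR decline is the obvious example.* Protocol Appendix 1 excludes expected progression of the disease from AEs unless it is more severe than expected. A Grade 3 or higher eGFR event is an AESI reportable within 24 hours of awareness, which should leave a dated trail. SAP 4.7.2 also summarizes laboratory values that meet the grading table separately. The exposure is clearer for clinical AEs that have no dated laboratory series behind them.

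**What to change.** Before the final database lock, identify AEs ongoing at the first IMP dose or at the first open-label dose. For these, obtain by query the date and grade of any later worsening, entered as a linked record or as a dated grade change on the existing one.

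Add to SAP 4.7.2 or the addendum that treatment emergence and maximal severity within each period are derived from that date, with each participant still counted once per period. If the eCRF already dates grade changes, no queries are needed and a sentence saying so, together with the derivation rule, is enough.

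The cost is a small set of site queries limited to AEs that span the two dates, and a short addition to the analysis text.
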